All statistical analyses will be conducted by the Research Core of the Maya Angelou Center for Health Equity. The main hypothesis being tested involves evaluating the mean differences in changes in HbA1c at one year. Secondary outcomes include changes in clinical characteristics and biochemical lab results and biomarkers of insulin sensitivity. Statistically, all of these analyses could be treated in a similar fashion after appropriate transformations are made to satisfy assumptions made about the distribution of residuals. We will apply a repeated measures analysis of variance to changes (collected across the planned visits at 6, 12, 18, and 24 months) to address intra-individual correlations, which accommodates interim testing and allows participants with incomplete patterns to contribute to the analysis and evaluation²⁴. Our analysis adopts the intention-to-treat approach. Inference for primary comparisons will be two-sided, with significance level alpha = 0.05. We will use repeated measures analysis of covariance in which indicators for visit are included to control for systematic temporal differences that may occur that are common to both intervention conditions. We test differences from baseline (rather than using baseline levels as a covariate in analyses of post-randomization values), as it is these differences that are the focus of our intervention and to limit the bias associated with estimates from regression models that include fallible covariates. Random effects terms will be used to model differences as these have been shown to yield inferences of more appropriate size than fixed effect models. Compound symmetry models will be used to model intra-subject

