longitudinal covariance and models will be fitted via maximum likelihood. The primary comparison will be based on a Wald statistic. We will not include additional covariates or stratification in the primary comparison, however, we will describe any chance differences between cohorts and, in supporting analyses, covary comparisons on any baseline factors that appear to be unbalanced. When we are developing the ANCOVA models, we will determine whether the assumptions of general linear models are satisfied. Diagnostics and residual plots will be reviewed to ensure that the assumptions are met. Should assumptions be violated, transformations of the outcome data will be considered: the order of the priority in choosing a transformation will be to satisfy the (1) linearity assumption, (2) homogeneity assumption (homoscedasticity), and (3) normality assumption. As mentioned above, secondary (supporting) analyses will assess the influence of covariates on the mean differences and to explore whether mean differences vary over follow-up time (using interaction terms). In addition, we will explore the homogeneity of LHAs with respect to outcome measures using hierarchical mixed models in which LHAs are coded as random effects and participant data are nested within LHAs. Such models will allow us to place confidence bounds on the contributions of LHA differences to overall variability.

Sample Size and Power

In this section we justify our plans to recruit and follow 225 participants who will be randomized with equal probability to either the intensive lifestyle intervention or individual education arm. Our goal is to provide greater than 80% statistical power to detect an average difference of .25 standard deviations from baseline in HbA1c between the two groups at one year. With a sample size of 225 participants, we will have 85-88% power to detect a net intervention effect of .25%. These estimates include allowance for a 5% loss to follow-up rate every 6 months. Although the DPP has not published any data that allow us to estimate the standard deviation and longitudinal correlation of HbA1c, similar studies conducted for a longer period of time have estimated the average change in A1c to be .74% with a standard deviation of 1.25% for an effect size of .59.

V. Human Subjects Protection

A. Potential Risks to Subjects

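### Measurement error in baseline HbA1c is no reason to leave it out of a randomised comparison; pre-specifying it costs almost nothing and brings a small, assumption-dependent gain in precision

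*Combined protocol and SAP*

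**What the plan says.** Section IV (Analytical Plan) sets the target: "The main hypothesis being tested involves evaluating the mean differences in changes in HbA1c at one year". The model is a repeated-measures analysis of change at 6, 12, 18 and 24 months, and baseline is deliberately kept out: "We test differences from baseline (rather than using baseline levels as a covariate in analyses of post-randomization values". Two reasons follow. The first is "as it is these differences that are the focus of our intervention". The second is "to limit the bias associated with estimates from regression models that include fallible covariates".

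The same section then says "We will not include additional covariates or stratification in the primary comparison". Adjustment appears only in secondary work. The plan will, "in supporting analyses, covary comparisons on any baseline factors that appear to be unbalanced", and its "secondary (supporting) analyses will assess the influence of covariates on the mean differences". It also says that the other outcomes could be handled in the same way, so the choice carries over to them.

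**The concern.** The second reason comes from settings where the groups differ systematically at baseline. There, an error-prone covariate under-corrects and the group contrast is biased. Section III.E.b randomises individuals, so the groups differ at baseline only by chance.

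The reason is also at odds with the rest of the plan. A change score subtracts the same error-prone baseline with its coefficient fixed at 1, so it does not escape the error. The supporting analyses would adjust for measured baseline factors that may be equally fallible.

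The first reason is a legitimate preference, and adjustment does not defeat it. If change is regressed on arm plus baseline, the arm coefficient is still a difference in change.

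At stake are some precision, the sensitivity of the primary estimate to chance imbalance, and an adjustment rule that waits to see which factors look unbalanced.

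**Working it through.** **Inputs.** From the documents: 225 randomised, 2:1 (III.E.b), 5% loss every 6 months, two-sided 0.05, effect 0.25 percentage points, SD of change 1.25%. Not in the documents, so assumed: baseline SD s0 of 0.20–0.30 (a uniform spread over the 5.7–6.5% entry window gives 0.8/√12 = 0.23) and slope b of follow-up on baseline of 0.5–0.7, common to both arms.

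**1. The plan's power figure.** Sample Size and Power states "we will have 85-88% power to detect a net intervention effect of .25" percentage points.
- Completers at one year: 225 × 0.95² = 203, or 135 and 68 at 2:1. √(1/135 + 1/68) = 0.1487.
- At SD 1.25: SE = 1.25 × 0.1487 = 0.186, and power is about 27%. The stated figure does not reproduce.
- Back-solving at 2:1: SD = 0.25 / [(1.960 + 1.036) × 0.1487] = 0.561 for 85%, and 0.25 / [(1.960 + 1.175) × 0.1487] = 0.536 for 88%.
- I carry two cases: SD 0.545 (SE 0.081, power 87.0%) and SD 1.25.

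**2. Is the adjusted contrast biased?** Arm is independent of measured baseline, so no bias is expected. Simulation (20,000 trials per setting; true effect −0.25, s0 0.30, residual SD 0.50, true slope 1) at baseline reliability 0.5, 0.7 and 0.9 gave:
- adjusted means −0.2506, −0.2502, −0.2490;
- unadjusted means −0.2506, −0.2503, −0.2490;
- Monte Carlo SE at most 0.0006.

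A further null simulation at reliability 0.8, with and without selection on a screening HbA1c of 5.7–6.5%, rejected in 5.3–5.4% of trials adjusted and 4.8–5.3% unadjusted.

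**3. Precision with a common slope.** Var(change) − Var(adjusted) = s0²(1−b)². For s0 0.30 and b 0.5 this is 0.09 × 0.25 = 0.0225, and 0.0225/0.545² = 7.6%. Estimating one slope inflates variance by about 1/(203−4) = 0.5%; the net columns include this, the power column does not.

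| b | s0 | Saving, SD 0.545 | Power | Net | Saving, SD 1.25 | Net |
|---|---|---|---|---|---|---|
| 0.5 | 0.20 | 3.4% | 88.1% | 2.9% | 0.6% | 0.1% |
| 0.5 | 0.23 | 4.5% | 88.4% | 4.0% | 0.9% | 0.3% |
| 0.5 | 0.30 | 7.6% | 89.4% | 7.1% | 1.4% | 0.9% |
| 0.7 | 0.20 | 1.2% | 87.4% | 0.7% | 0.2% | −0.3% |
| 0.7 | 0.23 | 1.6% | 87.5% | 1.1% | 0.3% | −0.2% |
| 0.7 | 0.30 | 2.7% | 87.8% | 2.2% | 0.5% | 0.0% |

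At SD 1.25, power stays at 27.0–27.3%. At b = 1 there is no saving. At SD 0.545 the net gain vanishes at b = 1 − √0.005 × 0.545/s0, that is 0.81 to 0.87. The SD 0.545 inputs imply a baseline-to-follow-up correlation of only 0.18–0.36.

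**4. Chance imbalance.** A baseline difference of 1.96 SE (about 1 trial in 20) is 1.96 × s0 × 0.1487 = 0.058 to 0.087. It shifts the unadjusted estimate by (1−b) times that amount. At b 0.5 the shift is 0.029–0.044 (0.36–0.54 of the SE of 0.081); at b 0.7 it is 0.018–0.026 (0.22–0.32 SE). In the simulation of step 2, the unadjusted estimate moved by −0.50, −0.30 and −0.09 per unit of imbalance, and the adjusted one by at most 0.01.

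**5. Unequal slopes, no arm-by-baseline term.** At 2:1, Var(change) − Var(adjusted) = s0²(1−b̄)(1−bC)(1/135 + 1/68), with b̄ the size-weighted mean slope and bC the control slope. It is negative only if b̄ and bC lie on opposite sides of 1.
- Slopes 0.5 (lifestyle) and 1.2 (control), s0 0.30, residual SD 0.56: b̄ = 0.733, and 0.09 × 0.267 × (−0.2) × 0.0221 = −0.000106 against a change variance of 0.00715, a loss of 1.5%.
- Slopes 0.3 and 1.2, residual SD 0.30: b̄ = 0.6, and −0.000159 against 0.00237, a loss of about 7%.
- With a centred arm-by-baseline term the large-sample variance ratios are 1.000 and 0.991.

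**The case against.** The strongest reply is that both estimators are valid, the plan's first reason alone supports its choice, and the gain is negligible at the only SD documented. That is largely right. It is why this is a recommended improvement and not a validity finding. It does not rescue the second reason.

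Other points, and what stands:
- **Assumed inputs.** True: s0 and b appear nowhere. The SD of 0.545 is solved at 2:1, whereas the power section says equal probability. At 1:1 with 203 completers the SD would be 0.568–0.594, and the largest saving 6.4–7.0% instead of 7.6%. Equal baseline and follow-up variances with correlations of 0.5–0.9 would give 5–25%. At correlation 0.5 and change SD 0.545, that needs a baseline SD of 0.545, while values confined to a window 0.8 wide cannot exceed 0.40. A separately measured baseline could spread further, so the smaller range is the cautious one.
- **Dropout.** Independence holds as randomised, not necessarily among those retained. Under simulated arm-differential dropout of about 10% driven by true baseline, the adjusted estimate was biased by about 0.01 to 0.04 and the change score was not. When dropout followed measured baseline, the change score was biased by 0.01–0.03. This is a fair qualification, but it cuts both ways.
- **Chance imbalance is already covered.** Partly. The supporting analyses address it, and the unadjusted interval allows for it on average. The primary estimate still carries the shift.
- **Single visit only.** Correct: the figures above are for the one-year contrast. None is offered for pooled visits or secondary outcomes.

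**Conclusion.** The concern holds. The fallible-covariate reason does not apply to this randomised comparison and should be corrected whichever model is kept. The change analysis is unbiased with correct type I error as far as the baseline choice goes.

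The net precision gain at one year is about +0.7% to +7.1% of variance if the SD of change is near 0.545, and −0.3% to +0.9% if it is 1.25. Both ranges assume s0 0.20–0.30, a common slope of 0.5–0.7 and 135 versus 68 completers. The gain is nil at slope 1 before the cost of estimating the slope. It can become a loss if the control slope and the mean slope straddle 1 and no arm-by-baseline term is fitted.

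Adjustment does not repair the power statement or the conflict between 2:1 and equal allocation; those are separate matters. Confidence in the size is medium; the point about bias does not depend on these inputs.

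**What to change.** - Delete the fallible-covariate reason from section IV.
- Pre-specify the baseline value of the outcome, with baseline-by-visit terms, in the primary and secondary repeated-measures models. Change can remain the response. Amend the sentence that bars covariates from the primary comparison to match.
- If protection against unequal slopes is wanted, add a mean-centred arm-by-baseline term. With it the large-sample variance is no larger than that of the change analysis.
- If an outcome is transformed, enter its baseline on the same scale.
- Keep the unadjusted change analysis as a sensitivity analysis, and the existing supporting analyses for other baseline factors.

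The cost is SAP wording and a few degrees of freedom: one slope per visit, or two with the arm-by-baseline term, at about 0.5% of single-visit variance for one slope. Table 3 in section III.H already schedules baseline HbA1c, glucose, lipids, weight and blood pressure, so no new data are needed.

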- Other Chronic Conditions: Other chronic disease likely to limit lifespan to less than 2-3 years, including any cancer requiring treatment in past 5 years except non-melanoma skin cancer.
- Medication: Chronic use of medicine known to significantly affect glucose metabolism (e.g., corticosteroids, protease inhibitors).
- Other: Conditions/criteria likely to interfere with participation and acceptance of randomized assignment, including the following: inability/unwillingness to give informed consent, another household member already randomized to La Comunidad, major psychiatric or cognitive problems (schizophrenia, dementia, self-reported active illegal substance or alcohol abuse), participation in another research study that would interfere with La Comunidad.

E. Screening and Randomization

a. Tiered Screening Process

A tiered screening process will be implemented to maximize the efficiency of screening. Interested prospective participants will be identified at the churches, community events, or by advertising, and will complete or be administered an initial pre-screening tool to assess medical history and the diabetes risk screening tool developed by the American Diabetes Association²². If potentially eligible, they will then be invited to take part in an interactive question and answer session to learn more about the study, followed by the informed consent process. Those participants still interested and eligible will then have their height, weight, and blood pressure measured and will complete the physical activity readiness questionnaire (PAR-Q). Those participants who have met all other eligibility criteria will then have a blood draw to determine HbA1c. Figure 2 outlines the screening process that we plan to implement.

Figure 2. Tiered Screening Process for La Comunidad

b. Randomization

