Blood pressure will be measured using an automated device (Omron HEM 907XL) following standardized procedures as outlined in current clinical practice guidelines. Use of an automated device reduces measurement variability and errors. The presence of hypertension at baseline and follow-up will be assessed using a combination of BP measurement, self-reported diagnosis and use of antihypertensive medication.

c. Medical History

During screening, medical history of diabetes, cardiovascular disease and other medical conditions will be obtained to evaluate the inclusion and exclusion criteria. During follow-up, new diagnoses of diabetes, cardiovascular disease, hypertension and other chronic diseases, unexpected problems, serious adverse events will be tracked. Deaths will be identified by following up missed appointments with contacts to the participant's residence and informants.

d. Laboratory Measures

Phlebotomy will be performed by trained, certified phlebotomists. Specimen collection at baseline and follow-up visits will be performed following at least an 8 hour fast (typically over night) in accordance with American Diabetes Association guidelines. Blood samples for plasma glucose will be collected in vacutainers containing sodium fluoride in order to minimize post collection changes due to glycolysis and will be stored at room temperature until processed. Samples for HbA1c, glucose, insulin, and lipids will be collected and transported to the local LabCorp facility for analysis. Communications with LabCorp and requisitions for these assays will be facilitated through the CRU's existing contract with LabCorp. Plasma and serum samples will be retained for future analysis of CRP, IL-6, leptin, adiponectin, expression of IL-8 in circulating mononuclear cells, Omega 3 and 6 fatty acids, free fatty acids. We will also collect sufficient blood samples to isolate DNA and may perform genome-wide association studies (GWAS). These analyses are included in the specific aims, but samples with which to conduct these analyses will be stored in [name] laboratory until additional funding can be obtained.

e. Diet Assessment

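### The primary HbA1c analysis uses one of the two pre-randomisation HbA1c values and adjusts for neither, so the arm difference is somewhat less precise than the collected data allow

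*Combined protocol and SAP*

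**What the plan says.** **First value.** Section III.E.a (Tiered Screening Process) places an HbA1c test last in screening: "Those participants who have met all other eligibility criteria will then have a blood draw to determine HbA1c". The screening form in Appendix B has a numeric field for the result and excludes values outside 5.7-6.5%.

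**Second value.** Section III.H (Data Collection) puts screening in community locations and the baseline visit later, at a clinical facility. Table 3 lists an HbA1c at that visit and at 6, 12, 18 and 24 months. Section III.H.d, on baseline and follow-up specimens, says: "Samples for HbA1c, glucose, insulin, and lipids will be collected and transported to the local LabCorp facility for analysis". Randomisation follows the baseline assessment (sections III.A and III.E.b), so both draws precede it.

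**Analysis.** Section IV states: "The main hypothesis being tested involves evaluating the mean differences in changes in HbA1c at one year". Change is the outcome: "We test differences from baseline", "rather than using baseline levels as a covariate in analyses of post-randomization values". One reason given is to limit "bias associated with estimates from regression models that include fallible covariates". It adds: "We will not include additional covariates or stratification in the primary comparison".

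The documents do not say what becomes of the screening value after eligibility, which assay or laboratory produced it, or how long before baseline it was drawn.

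**The concern.** A change score subtracts the baseline value with a coefficient of exactly 1. The biological and assay error of that one draw therefore enters the change at every follow-up visit at full weight. The plan recognises that the baseline is measured with error, and gives this as a reason not to adjust for it. Subtracting it does not remove the error. A second pre-randomisation measurement of the same quantity carries information about the participant's true starting level, and the plan does not use it.

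At stake is the width of the confidence interval for the primary arm difference, and hence power. The validity of the test is not at stake.

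**Working it through.** **1. The plan's own figure.** Sample Size and Power states 85-88% power for an effect of 0.25% with 225 participants and 5% loss per 6 months. At 12 months, 225 × 0.95² = 203 remain. Two-sided alpha is 0.05. Power = Φ(δ / [σ√(1/n₁ + 1/n₂)] − 1.96), where √(1/n₁ + 1/n₂) is 0.140 at 1:1 (the power section) and 0.149 at 2:1 (section III.E.b).

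- Effect of 0.25 SD: 43% (1:1), 39% (2:1).
- Effect of 0.25% with the quoted SD of 1.25%: 30%, 27%.
- Effect size 0.59: 99%, 98%.

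None gives 85-88%. Reaching it needs an unstated SD of change of 0.57-0.59 (1:1) or 0.54-0.56 (2:1). That is a separate defect. It means that gains here can only be given in relative terms.

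**2. Adjustment does not bias the arm difference.** With baseline B, screening value S and follow-up Y, the adjusted estimate is the difference in mean Y, minus b₁ × (difference in mean B), minus b₂ × (difference in mean S). B and S precede randomisation, so both differences have expectation zero. Measurement error shrinks b₁ and b₂ but leaves that unchanged. A laboratory offset, or regression to the mean after the eligibility cut, is common to both arms. The plan's change score is the special case b₁ = 1, b₂ = 0.

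**3. Precision without the eligibility cut.** Let r be the baseline to 12-month correlation and q the screening to baseline correlation. Variances relative to single-baseline change, 2(1 − r), are:

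- adjusting for B: (1 − r²) / [2(1 − r)] = (1 + r)/2;
- adjusting for both: [1 − 2r²/(1 + q)] / [2(1 − r)].

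With r = 0.7 these are 0.85 for B alone, and for both 0.71 (q = 0.7) or 0.81 (q = 0.9).

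**4. Precision with the cut.** Selecting on S weakens its value, so the cut was simulated. The table shows variance relative to single-baseline change (assumed population mean 5.7%, true SD 0.4). The noise ratio is screening error variance divided by baseline error variance.

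| Within-person SD | SD of true change | Noise ratio | Average of S and B | Adjust for B | Adjust for both | Further cut from S |
|---|---|---|---|---|---|---|
| 0.10 | 0.1 | 1 | 0.830 | 0.939 | 0.828 | 12% |
| 0.10 | 0.3 | 1 | 0.954 | 0.983 | 0.954 | 3% |
| 0.20 | 0.1 | 1 | 0.756 | 0.808 | 0.745 | 8% |
| 0.20 | 0.3 | 1 | 0.871 | 0.898 | 0.865 | 4% |
| 0.10 | 0.1 | 3 | 0.970 | 0.949 | 0.905 | 5% |
| 0.20 | 0.3 | 3 | 0.929 | 0.915 | 0.906 | 1% |

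The last column is 1 − (both)/(B alone); for example, 1 − 0.828/0.939 = 12%.

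Over the wider grid (true SD 0.3-0.4, within-person SD 0.10-0.25, SD of true change 0.1-0.5, equal error, values rounded to 0.1), adjusting for both lowers variance by 2-29%. The standard error falls by 1 − √0.98 = 1% to 1 − √0.71 = 16%. The screening value's own share is 1-13% of variance.

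**5. Averaging as an alternative.** With independent errors, averaging replaces baseline error variance e² by (e_S² + e²)/4. It helps only while e_S² is below 3e². In simulation it was up to 7% worse in variance than the single baseline when screening error variance was five times larger. Adjusting for both never lost precision.

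**The case against.** Change from one scheduled baseline visit is a legitimate prespecified analysis. It causes no bias and no inflation of type I error. That stands, and the point is confined to efficiency.

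The gains are also largest where they are least needed. With within-person SD 0.25 and SD of true change 0.1, the SD of change is √(2 × 0.0625 + 0.01) = 0.37, and power for 0.25% at 2:1 is already about 99.5%. At the SD of change that the stated power requires (0.54-0.59), averaging with equal errors saves 0.5e²/σ². That runs from 0.005/0.348 = 1.4% (e = 0.10) to 0.03125/0.292 = 10.7% (e = 0.25). If the quoted 1.25% is itself the SD of change, the saving is only 0.3-2.0%. This stands and keeps the point modest.

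Three stronger readings are tempting, and the documents support none of them:

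- **A fixed 25% gain.** If all raw values, screening included, had equal correlations, averaging would cut the variance from 2σ²(1 − r) to 1.5σ²(1 − r) for any r. But the plan applies compound symmetry to the follow-up changes and never models the screening value. With independent errors, equal correlations would also require that true change does not vary between people.
- **A gain worth about 79 participants.** A 26% variance cut gives 225/0.74 − 225 = 79. This takes the favourable end of an assumed range, where power is already ample.
- **Participants lost through failed baseline samples.** The documents give no failure rate; their 5% per 6 months is loss to follow-up.

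Finally, adjusting for both values reverses the plan's choice not to use covariates. That is true, but the measurement-error reason for that choice does not apply to a randomised arm comparison.

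**Conclusion.** The point holds as a modest loss of efficiency. Two HbA1c values precede randomisation, and the primary analysis uses one of them, by plain subtraction, with no adjustment. That the screening value goes unused is inferred from the plan's silence together with its no-covariate rule.

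The 2-29% total gain and the 1-13% share from the screening value rest on assumed variances and equal assay error. The share is smaller if the screening assay is noisier. Much of the total comes from adjusting for the baseline value at all, so the screening value should not be credited with the whole range. A reader might infer that averaging the two values is the natural remedy. The documents do not support that, because the screening assay and interval are unstated, and averaging in a value selected to lie within 5.7-6.5% would distort the reported within-arm change.

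**What to change.** In section IV, make the primary repeated-measures HbA1c model adjust for both the baseline-visit and the screening HbA1c. Both are needed: adding the screening value alone to a change score gained nothing. The outcome can remain change from the baseline visit, since adjusting change for baseline gives the same arm effect as adjusting the follow-up value. Report unadjusted change from the baseline visit as a sensitivity analysis. State which assay and laboratory produced the screening value and the usual interval to baseline, and average the two values only if assay and laboratory were the same.

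The cost is a short amendment to the analysis text, with no new data. The no-covariate rule and the fallible-covariate reason must be revised, and within-arm change must be reported separately.

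### Only the lifestyle arm is treated in about 11 LHA-led groups, but the primary model names no group or LHA term, so its standard error is too small if outcomes cluster by group

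*Combined protocol and SAP*

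**What the plan says.** **Design.** III.E.b Randomization plans 225 participants in 11 waves, allocated 2:1, with about 14 lifestyle participants per wave and 11 LHA-led groups in all. Table 2 of III.F.b gives weekly LHA-led group meetings for six months, then one monthly contact that alternates between a group meeting and a call from the LHA. III.G gives the comparison arm two individual dietitian sessions and a newsletter. Individuals are randomized, but only one arm is treated in groups.

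**Primary model (IV. Analytical Plan).** It is a repeated-measures model of change from baseline with visit indicators. "Compound symmetry models will be used to model intra-subject" longitudinal covariance, "models will be fitted via maximum likelihood", and "The primary comparison will be based on a Wald statistic". The plan also says: "We will not include additional covariates or stratification in the primary comparison". Just before the covariance statement it says "Random effects terms will be used to model differences", without saying whether these are at the level of the person, the group, the LHA or the wave.

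**LHA effects.** These come in a separate, additional analysis: "we will explore the homogeneity of LHAs with respect to outcome measures using hierarchical mixed models in which LHAs are coded as random effects". Its stated purpose is to "place confidence bounds on the contributions of LHA differences to overall variability". It does not promise an arm difference adjusted for group, and it does not say how comparison participants, who have no LHA, enter the model.

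**The concern.** This is a partially nested design. People who meet weekly in the same group under the same LHA may come to resemble each other in HbA1c change. The plan's own rationale points that way: III.B draws on group dynamics, and III.F.d describes problems being worked through with help from the group. A model that treats all lifestyle participants as independent leaves this variance out of the standard error of the arm difference. The confidence interval is then too narrow and the test rejects too often.

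A second source can act in the other direction. If participants recruited in the same wave share part of their change in both arms, that part largely cancels from the arm difference. It still sits in the residual variance of a model with no wave term, so the reported SE is then slightly too large.

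**Working it through.** **Inputs**

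- 150 lifestyle and 75 comparison participants (225 at 2:1), 11 waves, 11 groups: III.E.b. The power paragraph's "randomized with equal probability to either the intensive lifestyle intervention or individual education arm" conflicts with this. I use 2:1 because the wave and group counts are built on it.
- 5% loss per 6 months (Sample Size and Power), so 0.95 × 0.95 = 0.9025 are retained at one year. Then n1 = 150 × 0.9025 = 135.4, n0 = 75 × 0.9025 = 67.7, and group size m = 135.4/11 = 12.31.
- Two-sided alpha of 0.05: IV. Analytical Plan.
- Group ICC and wave ICC: not documented. I assume 0.01-0.05 for group and 0.03-0.10 for wave.

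The plan has no figure on clustering to reproduce: its power paragraph gives no ICC and no design effect. Its 85-88% power is not used here.

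**Step 1: group variance only, one 12-month score**

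Let f = 1/135.4 + 1/67.7 = 0.02216. The lifestyle-arm design effect is DE = 1 + (12.31 − 1) × ICC. The ratio of true to reported SE is √[(DE/135.4 + 1/67.7)/f], and alpha is 2 × [1 − Φ(1.96/ratio)].

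| Assumed group ICC | DE | True/reported SE | Alpha |
|---|---|---|---|
| 0.01 | 1.113 | 1.019 | 5.4% |
| 0.02 | 1.226 | 1.037 | 5.9% |
| 0.05 | 1.565 | 1.090 | 7.2% |

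This holds total variance equal in the two arms. Holding residual variance equal instead gives ratios of 1.017, 1.035 and 1.085 and alpha of 5.4%, 5.8% and 7.1%.

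**Step 2: shared wave variance only**

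With arms balanced within waves, reported/true SE = 1/√(1 − ICC). At a wave ICC of 0.05 this is 1/√0.95 = 1.026, and alpha falls to about 4.4%.

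**Step 3: both together**

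Write Vg for group variance and Vw for wave variance.

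- The true variance of the arm difference gains Vg/11 = 0.0909 Vg, because wave effects cancel.
- The pooled residual has (135.4 − 1) + (67.7 − 1) = 201.1 df. The between-group part of the lifestyle arm contributes (135.4 − 12.31)/201.1 = 0.612 of Vg. Waves in both arms contribute 0.918 of Vw.
- The reported variance therefore gains 0.02216 × (0.918 Vw + 0.612 Vg) = 0.02035 Vw + 0.01357 Vg.

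The SE is understated when Vg/Vw exceeds 0.02035/(0.0909 − 0.01357) = 0.26. Without the finite-wave correction the threshold is 0.29.

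**Step 4: simulation**

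The simulation uses 11 waves, 150/75 participants, 9.75% loss, one 12-month score and 40,000 trials per setting (Monte Carlo SE 0.1 point). The REML fits use Satterthwaite df and drop components estimated at zero. Entries are alpha in percent.

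| Wave ICC | Group ICC | Plan (ML, Wald z) | Group intercept only | Wave and group |
|---|---|---|---|---|
| 0 | 0 | 5.3 | 4.5 | 4.6 |
| 0 | 0.01 | 5.6 | 4.5 | 4.7 |
| 0 | 0.02 | 6.2 | 4.8 | 5.2 |
| 0 | 0.05 | 7.4 | 5.0 | 5.4 |
| 0.05 | 0 | 4.7 | 3.1 | 4.1 |
| 0.03 | 0.02 | 5.9 | 3.7 | 4.5 |
| 0.10 | 0.02 | 5.2 | 2.0 | 4.2 |

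A separate run of the plan's test gave 5.3% with no clustering, 5.9% at group 0.02, 7.5% at group 0.05 and 4.7% at wave 0.05 only. The group-only intercept is conservative when waves vary, because with about one group per wave it absorbs the wave variance.

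**The case against.** - **The random-effects sentence may already cover groups.** It is justified by the size of the test and stands apart from the within-person covariance sentence, so it could mean a unit other than the person. That reading is possible. But no unit is named, and LHA effects are introduced later as something additional and exploratory. The group is not in the primary comparison as written.
- **A reader might infer that the plan forbids a group term, because it refuses additional covariates or stratification.** The documents do not support this. The same sentence contrasts that refusal with later adjustment for unbalanced baseline factors. A random design term is neither a covariate nor stratification.
- **A reader might infer that LHA variation is ignored.** It is not: the exploratory model would estimate it. What is missing is its effect on the primary SE.
- **Group variance may be small.** Content is on DVD, LHAs are certified, and weekly meetings end at month 6 while the main comparison is at one year. This stands as a reason to expect a low ICC. But all later group and telephone contacts still run through the LHA.
- **Wave variance has no support in the documents.** This stands. Analysing change from baseline also removes stable differences in level between waves.
- **The joint model is not uniformly better.** In the full set of nine simulated settings, an independent-errors t test was nearer 5% in five, tied in one and further away in three. The joint model is clearly better only with group variance alone at 0.02 or 0.05. This also stands; the case for it is protection against inflation, not a gain everywhere.
- **A reader might infer severe inflation.** A four-visit simulation reached 9.2%, but only with group ICC 0.05, no wave variance, an assumed within-person correlation of 0.5, a group effect constant at all four visits, and no shortening of follow-up for late entrants, which III.H does provide for. It is a worst case.

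**Conclusion.** The point holds in a limited form. The design is partially nested and the primary model, followed as written, carries no group or LHA term. Whenever group variance in the lifestyle arm is material and not offset by wave variance, the primary SE is too small. The 2-9% understatement rests on an assumed ICC, on 11 equal groups and on a single 12-month score. At the low end it hardly matters.

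The number of distinct LHAs is not stated. If, for illustration, six LHAs led all the groups, m = 135.4/6 = 22.56 and at ICC 0.05 DE = 1 + 21.56 × 0.05 = 2.078. The ratio is then √[(2.078/135.4 + 1/67.7)/0.02216] = 1.166, with alpha about 9.3%.

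The documents do not show that the SE is in fact too small, only that the plan does not guard against it. The allocation conflict and the plan's power figure, which does not follow from its stated inputs, are separate problems and add no weight here. This is a cheap improvement that should be made, not a demonstrated failure of the analysis.

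**What to change.** In IV. Analytical Plan:

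1. State the level of the random effects.
2. Include in the primary model a random intercept for assigned lifestyle group (lifestyle arm only) together with a random intercept for recruitment wave (both arms). Use LHA as the unit if one LHA leads several groups. Do not use the group intercept alone.
3. Clarify that the sentence on covariates and stratification does not exclude these design terms.
4. Fit by REML with one named small-sample df method in place of ML with a Wald z. Satterthwaite is the one simulated here.
5. Pre-specify that a variance component estimated at zero is dropped.
6. Report both variance components.
7. Keep the independent-errors model as a sensitivity analysis.

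**Cost.** The change needs SAP wording and a record of each participant's wave, assigned group and LHA; attendance at the group meetings is already tracked (III.F.e). If there is no clustering, simulation puts the loss at about 2 points of power (83.2% against 85.0%, for an effect chosen to give 85% under the plan's test) and an interval about 3.5% wider. If wave variance is present the test is mildly conservative, with alpha of 4.1-4.5% in the settings tabulated. Median df was 47 at group ICC 0.05 and 34 at wave 0.10 with group 0.02. It approaches 10 if both variances are substantial, and fewer LHAs than groups would mean fewer clusters.
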